Waist Circumference	A tape measure with instructions will be provided to the participant to measure at the designated timepoints.	X	X	X
Fasting Blood Draw	The collection will include: complete metabolic and lipid panel, uric acid, ApoB, GGT, glucose, insulin, HbA1c. These are biomarkers that are risk factors for poor metabolic health, diabetes, and cardiovascular disease	X		X
BevQ	This questionnaire seeks to quantify the frequency, type and volume of beverages consumed at work and home.	X	X	X

**SUTTER HEALTH
INSTITUTIONAL REVIEW BOARD**

Protocol Summary Form

ASA 24	This is a web-based, 24-hour dietary recall tool developed by the National Cancer Institute	X	X	X
Stanford Leisure Time Scale (L-CAT)	This is a scale that measures physical activity.	X	X	X
*PROMIS4a Depression	Assesses the presence and severity of symptoms of depression.	X	X	X
Beverage Craving Questionnaire (FCQ-T-R)	Assesses the following: 1) preoccupation with sweetened beverages; 2) loss of control; 3) positive outcome expectancy; 4) emotional cravings	X		
Reward Based Eating Drive (RED-13)	Assesses three aspects of drive to eat: 1) loss of control; 2) lack of satiety; 3) preoccupation with food	X	X	X
Perceived Stress Scale	This is a widely used questionnaire to assess stress levels. It evaluates the degree to which an individual has perceived life as unpredictable, uncontrollable, and overloading over the previous month.	X	X	X
Copenhagen Burnout Inventory (CBI)	This six-item inventory measures personal burnout experienced by participants.	x	x	x
Self-Efficacy	These questions are used to determine if an individual exhibits intention to reduce SSB consumption.	X	X	X
Science of Behavior Change Texts Parent Grant	Assesses craving, psychological stress, consumption and self-efficacy (two texts/day x four days/week)	X	X	X
Science of Behavior Change Texts Supplemental Grant	Assesses craving, psychological stress, consumption and self-efficacy (two texts/day x four days/week)	Additional texts will be sent at the following time periods: 1, 2, and 3 months after SSB intervention.		
EPIC EMR	Lab results from the blood draw will be extracted from EPIC utilizing the resources of the Center for Health Services Research (CHSR). Limited data from the medical record will be extracted by CHSR that looks at metabolic health.	X		X
Incentive Gift		X	X	X

**SUTTER HEALTH
INSTITUTIONAL REVIEW BOARD**

Protocol Summary Form

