Using the Ecological Momentary Assessment (EMA) approach, cravings will be measured by study participants using smart phones. Using the REDCap platform, participants will receive a short set of questions at the following timepoints: baseline, 1, 2, and 3 months after SSB intervention starts at randomized affiliates, and 6 and 12-months. Two texts will be sent each day (morning and evening) four of the seven days of the week. Participants will be asked to quickly record the following: cravings (if any) for sugar sweetened beverages, psychological stress, consumption, and psychological stress. The primary target for this exploratory analysis is cravings for SSBs but we will also have access to information on whether or not subjects consumed SSBs in response to the craving. Each text should take one to-five minutes each. The content of the text is as follows:

- Introductory text at the start of each assessment period (Sunday afternoon) shall read:
 - o *Greetings Sweet Study Participant – this week, we’ll text you 4 clickable links in the morning and 4 in the evening on Tues, Thurs, Fri, and Sat. Each link will take 1-5 minutes to complete – Short and Sweet! The week after you finish the surveys, we’ll email you a \$10 gift code. Please complete at least 6 of the 8 texts in order to receive a gift code.*

Each day, the texts will be labeled as morning Sweet text 1, 2, 3, 4 and evening Sweet text 1, 2, 3, 4.

Location (asked in evening)

Today, were you physically working at your Sutter Health workplace?

**SUTTER HEALTH
INSTITUTIONAL REVIEW BOARD**

Protocol Summary Form

- Yes
- No

Can define a sugary drink here.

Craving Battery – Evening – Supplement and Parent

1. Today, did you crave a sugary drink? Yes / No

- If No, skip #2 and #3
- If Yes: Move on to #2.

2. At its most severe point, how strong was your craving for a sugary drink today?

Sliding bar, slider starting at middle or optimally nowhere and it gets placed when the respondent touches the screen, if starting in the middle then movement of bar required to advance to next question

**For #3, make these checkboxes, with the first two non-exclusive, and the “no” exclusive*

3. Did you drink anything in response to ANY of these cravings?

- Yes, a sugary drink
- Yes, water, a sugar-free drink, or a drink with no added sugar
- No

Psychological Stress Battery - Evening – Supplement and Parent

What was your overall mood like during the day?

1. I felt stressed, anxious, overwhelmed.

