2. I felt joyful, glad, happy.
3. I felt in control, coping well, on top of things.
4. I felt sad, downhearted, unhappy.

Scale:

0 = Not at all

1 = A little bit

2 = Somewhat

3 = Moderately

4 =Extremely

Consumption Battery – Evening, last item administered – Supplement

1. Thinking back on how much sugary drinks you had **today**, which is most true for you:

Response options: Assessment 1 (baseline)

- I drank less than I usually do
- I drank about as much as I usually do
- I drank more than I usually do

Response options: Assessment 2 and beyond
(1-month post-Ban and all further assessments)

**SUTTER HEALTH
INSTITUTIONAL REVIEW BOARD**

Protocol Summary Form

- I drank less than I usually did before the Sweet study
- I drank about as much as I usually did before the Sweet study
- I drank more than I usually did before the Sweet study

Self-Efficacy Battery – Morning

If going to work:

1) How sure are you that you will avoid drinking sugary drinks today while at your Sutter Health workplace?

Not sure at all ----- Extremely sure

Sliding bar, slider starting at middle or optimally nowhere and it gets placed when the respondent touches the screen, if starting in the middle then movement of bar required to advance to next question

- Don't know
- I don't plan to go to my Sutter Health workplace today

2) How sure are you that you will avoid drinking sugary drinks today while **not** at your Sutter Health Workplace?

[1] Not sure at all

[2]

[3] Somewhat sure

[4]

[5] Extremely sure

- I do not drink sugary drinks
- Don't know

Blood Draw

The orders for the blood draw will be signed off by [name] the study physician. Results will be sent to patients via My Health Online. The study participants will be asked to review out of range labs with their primary care physician

(4c) Methods of Data Analysis:

Analysis Plan for Aim 1: *How well does each intervention work alone?* We will assess the independent effects of the brief counseling intervention and workplace SSB sales ban on changes in primary and secondary outcomes.

Introduction: Aim 1 analyses will compare primary and secondary outcomes for employees exposed to the brief intervention only, the SSB sales ban only, and no intervention. Our operative hypothesis is that both the brief counseling intervention and sales ban will independently decrease HOMA and waist circumference relative to no intervention. Of four smaller studies testing the effects of brief SSB

**SUTTER HEALTH

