Analytic Plan for Aim 3: Participants will respond to a question asking if they experienced a craving for SSBs as *yes* or *no*. We will use this SSB craving variable (M), along with group assignment (X), to predict 12-month SSB consumption (Y). This simultaneous mediation model will comprise, first, a mixed effects logistic regression model (Path A in Figure 2 above, from X to M). This model will include random effects for day nested within study period, nested within person for each of the possible reports per day (morning, afternoon, evening, and “any other time not previously reported”). The dependent variable will be the dichotomous primary outcomes reflecting the experience of a craving or whether a craving was acted upon. Model covariates (fixed effects) include time of day, study period, randomization group, and the interaction of study period by randomization group. This will allow us to estimate the odds of having a craving or indulging in one at 6- and 12-months compared to baseline, separately for each experimental arm, as well as allowing for direct comparisons between study arms at each time point.

A second component of the model is a mixed effects linear regression model (Path B in Figure 2 above, from M to Y) that links a change in cravings between baseline and the 6-month follow up (measured as the change in the proportion of responses in which subjects reported cravings) to SSB consumption and HOMA at 12 months. We will perform this mediation model first without covariates¹¹⁵ and then will perform it with other predictors of SSB consumption (e.g., demographics, high-risk group) as in Aim 1. This analysis will allow us to estimate the proportions of variance in SSB consumption at 12 months that are related to changes in SSB craving experiences.

The relationship between the interventions and SSB consumption without the inclusion of craving (Path C) will have already been established in the analyses for Aims 1 and 2, so lastly, we will examine Path C' (interventions predicting consumption and waist change with the inclusion of the craving mediator). This will necessitate a model similar to those used in Aims 1 and 2, but with the addition of craving change and an interaction term for intervention*craving change.

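### Aim 3's Path A model expects up to four craving reports a day, but the texts ask about craving once, in the evening: the day-level variance cannot be determined in practice, and Path B's change score rests on at most four answers per wave

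*Combined protocol and SAP*

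**What the plan says.** **Model.** In section 4c, Analytic Plan for Aim 3, Path A is a mixed-effects logistic regression with "random effects for day nested within study period, nested within person for each of the possible reports per day (morning, afternoon, evening, and" a catch-all slot for other times). The fixed part is also set out: "Model covariates (fixed effects) include time of day, study period, randomization group, and the interaction of study period by randomization group". The outcome is whether a craving occurred or was acted upon. Path B then relates the baseline-to-month-6 change in each person's share of positive craving reports to 12-month SSB consumption and HOMA. The plan intends to report how much of the variance in consumption this change explains.

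**Data.** In section 4b, SSB Cravings and Stress Text Based Data Collection: "Two texts will be sent each day (morning and evening) four of the seven days of the week". The craving items are headed "Craving Battery – Evening – Supplement and Parent", and the yes/no item reads "Today, did you crave a sugary drink? Yes / No". The follow-up on whether a craving was acted upon sits in the same evening battery. The only battery labelled for the morning is "Self-Efficacy Battery – Morning", which has no craving item. The message to participants says "Please complete at least 6 of the 8 texts in order to receive a gift code". The study procedure table describes the texts as "Assesses craving, psychological stress, consumption and self-efficacy (two texts/day x four days/week") and does not say which text carries which items.

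**The concern.** The model and the instrument describe different data. Nothing in section 4b collects an afternoon, morning or other-time craving report.

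For Path A, a covariate with a single value is aliased with the intercept. A random effect for day, with one binary answer per day, is an observation-level effect that is identified only through the shape of the logit link. If it is kept, the conditional odds ratios depend on a variance that the data cannot settle.

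For Path B, a proportion built from four or fewer answers is a noisy measure of a person's craving frequency, and a difference of two such proportions carries the error of both. That error attenuates the unadjusted slope and the explained variance. A small or null indirect effect would then be hard to tell from a poorly measured mediator. Section 3 relies on Aim 3 to explain a success or to guide redesign after a failure, so that ambiguity matters. The plan makes no allowance for it.

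**Working it through.** **1. Count of reports (from section 4b).** Texts per wave: 2 × 4 = 8, which agrees with the participant message. Craving answers per wave: 1 × 4 = 4 at most. The model as written implies up to 4 × 4 = 16. Someone who completes exactly 6 of 8 texts and misses two evening ones has 4 − 2 = 2.

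**2. Can the day-level variance be seen?** The measure is twice the sample size times the Kullback-Leibler divergence between the true and the best-fitting model, which is the expected likelihood-ratio (LR) statistic. Random effects are integrated by Gauss-Hermite quadrature. All effects and variances here are assumed, because the documents give none.

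- *True day effect, fitted without one.* 700 people; period intercepts 0.3, −0.2, −0.7; person SD 1.5; person-by-period SD 0.7. With one report a day on four days in three waves, a true day SD of 0.5, 1.0 or 2.0 (logit scale) gives an expected LR of 0.02, 0.09 or 0.11. With four reports a day, even in a single wave, it gives 24, 243 or 1325. The term suits the data the model describes, not the data collected.
- *No true day effect, day SD fixed at 1 or 2.* 550 people (the plan's 12-month figure), 3 waves, 4 answers each; intercept −1.8 or 0; person SD / person-by-period SD 1.0/0.5 or 1.5/1.0; both follow-up waves shifted by −0.2; period-by-group odds ratio 0.60. All other parameters are re-optimised. Expected LR is 0.04 to 0.64 against a 5% critical value of 3.84. The fitted odds ratio becomes 0.55–0.56 (day SD 1) or 0.44–0.47 (day SD 2). Average fitted probabilities change by no more than 0.0005.
- *True day SD 1.* Fitting with day SD 0 or 2 gives an expected LR below 0.2, with odds ratios of 0.64–0.65 or 0.50–0.51.

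**3. Sampling error in Path B.** Ignoring between-person spread, the SE of one wave's proportion is √(p(1−p)/n). At p = 0.5 and n = 4 it is √(0.25/4) = 0.25, so the SE of a change is 0.25 × √2 = 0.35. With the 16 answers the model implies, it is √(0.25/16) × √2 = 0.18.

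**4. Reliability of the change score.** Let p be mean prevalence, S the SD of true change, r the between-wave correlation of true probabilities and n the answers per wave. Then

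- between-person variance per wave: V = S² / (2(1 − r))
- error variance of the change: E = 2(p(1 − p) − V) / n
- reliability: R = S² / (S² + E)

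The documents give none of p, S or r. The assumed ranges are p 0.2–0.5, S 0.15–0.30, r 0–0.5.

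- Lowest, n = 4 (p = 0.5, S = 0.15, r = 0): V = 0.01125; E = 2 × 0.23875/4 = 0.1194; R = 0.0225/0.1419 = 0.16.
- Highest, n = 4 (p = 0.2, S = 0.30, r = 0.5): V = 0.09; E = 2 × 0.07/4 = 0.035; R = 0.09/0.125 = 0.72.
- n = 2 at both waves, same two corners: 0.0225/0.2613 = 0.09 and 0.09/0.16 = 0.56.

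The expected unadjusted slope and explained variance are each multiplied by R. An assumed true share of 10% would appear as about 1.6% to 7.2% with 4 answers, or 0.9% to 5.6% with 2.

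**The case against.** The case against making much of this is fair in several respects.

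- **Path A's inference hardly changes.** In the four settings above with no true day effect, the expected LR for the period-by-group effect with the day SD at 0, 1 and 2 is 9.69/9.55/9.42, 6.75/6.71/6.67, 15.46/15.42/15.39 and 8.81/8.80/8.79. The shift in the odds ratio is a rescaling of the conditional effect, and a constant covariate would drop out of any fit. This stands. What remains is that the odds ratio the plan means to report is on a scale the data do not fix.
- **The day SD would be estimated, not fixed at chosen values.** True, but a likelihood this flat leaves the estimate close to arbitrary.
- **Path B's noise is separate from the wording mismatch, and its size is unknown.** Both parts stand. Few answers per wave would be a concern under a correctly written Path A too. Only the direction of the bias is certain. Two answers at both waves is a worst case, and the gift-code threshold is not an analysis rule.
- **The plan already warns that very small mediation effects may be missed.** It then says that no difficulty is expected, citing the pilot, and does not mention error in the mediator.
- **Other data exist.** The texts at months 1, 2 and 3 and the severity slider could help, but Path B as defined uses neither.
- **The study procedure table could be read as craving in both texts.** The battery labels are explicit, and even two reports a day would not match the model.

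**Conclusion.** The concern holds. The mismatch between the Aim 3 model and the text schedule is plain in the documents and rests on no assumption. With the evening-only schedule, the time-of-day effect cannot be estimated. The day-level variance is not identifiable in practice; strictly, the logit link leaves a trace of information. Period, group and period-by-group effects remain estimable, and fitted probabilities barely move. The Path A damage is confined to conditional odds ratios whose scale is undetermined: 0.60, about 0.55 or about 0.45 for one and the same effect under the assumed settings.

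In Path B, attenuation of the unadjusted slope and explained variance is certain in direction. Its size is not known: reliabilities of 0.16–0.72 (4 answers) and 0.09–0.56 (2 answers) are an illustration over assumed inputs, not bounds. The point should be corrected before analysis, but Aim 3 is exploratory and the primary analyses do not depend on it.

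**What to change.** 1. Reconcile the study procedure table and the text-schedule section in 4b with the Aim 3 plan in 4c, and state which craving-report schedule applies.
2. If evening-only is intended, restate Path A as a logistic mixed model for one evening report per day, with person and person-by-period random effects. Remove the time-of-day term and the day-level effect.
3. For Path B, add a sensitivity analysis corrected for measurement error and report the estimated reliability of the change score. State in advance that a null indirect effect will be read in the light of that reliability.
4. Optionally, use a joint or latent-variable model for the mediator, or bring in the severity slider and the month 1–3 waves already scheduled.

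The cost is a one-paragraph correction and some extra analysis of data already being collected. No text or visit changes if evening-only is what was meant. The drawback is that the error-corrected Path B estimate will have a wider interval than the raw one.

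### Aim 3 Path A: the acted-upon craving outcome is observed only on craving evenings, so comparing arms on it conditions on a post-randomisation event and can understate or reverse a benefit

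*Combined protocol and SAP*

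**What the plan says.** Path A in section (4c), Analytic Plan for Aim 3, is a mixed effects logistic model with two binary outcomes: "The dependent variable will be the dichotomous primary outcomes reflecting the experience of a craving or whether a craving was acted upon". Its stated target is the "odds of having a craving or indulging in one at 6- and 12-months compared to baseline". Estimates are planned within every arm, and the arms are also to be set directly against one another at each assessment. The fixed effects listed are time of day, study period, randomisation group, and the period-by-group interaction.

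The data come from the text-message items in section (4b), SSB Cravings and Stress Text Based Data Collection. The items sit under "Craving Battery – Evening – Supplement and Parent", and the schedule is: "Two texts will be sent each day (morning and evening) four of the seven days of the week". Item 1 asks whether the participant craved a sugary drink that day. Its routing is "If No, skip #2 and #3". Item 2 is craving strength. Item 3 is the acted-upon question: "Did you drink anything in response to ANY of these cravings".

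The Aim 3 hypothesis in section 1 and the Aim 3 expected outcomes in section (4c) both predict that cravings will fall, most of all in the multilevel arm. No section says how evenings without a craving enter the acted-upon model.

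**The concern.** Because of the routing, item 3 is blank by design on every no-craving evening. Unless a rule codes those blanks, a logistic model for item 3 uses craving evenings only. Whether an evening counts as a craving evening is decided after randomisation, and the trial expects it to differ by arm. The craving evenings left in a treated arm may then differ in kind from those in the control arm, for example by being stronger on average. None of the listed covariates deals with this. Craving strength is not among them, and it is skipped on the same evenings.

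At stake is the reading of the second craving measure. An intervention that mainly prevents weak, easily resisted cravings could appear to make people give in more often. Section 3 says the mediation analyses should show why the intervention worked, or help to build a better one. A misleading result on this measure would work against that.

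**Working it through.** The plan gives no rate, power or sample size for the acted-upon outcome, so there is no figure of its own to reproduce. All craving and acting rates below are assumptions.

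**Formulas.** Let w and s be the shares of evenings with a weak and a strong craving, and a_w and a_s the chances that each is acted on.
- Over all evenings: P(craved and acted) = w·a_w + s·a_s
- Among craving evenings: P(acted | craving) = (w·a_w + s·a_s) / (w + s)
- OR = odds in the intervention arm / odds in the control arm

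**Illustration.** Control: w = 0.30, a_w = 0.30, s = 0.30, a_s = 0.70. The intervention cuts w to 0.10 and changes nothing else.
- Control: 0.09 + 0.21 = 0.30 over all evenings; 0.30/0.60 = 0.50 among craving evenings.
- Intervention: 0.03 + 0.21 = 0.24 over all evenings; 0.24/0.40 = 0.60 among craving evenings.
- OR among craving evenings = (0.60/0.40)/(0.50/0.50) = 1.50.
- OR over all evenings = (0.24/0.76)/(0.30/0.70) = 0.74.

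**Range.** A second control arm: w = 0.40, a_w = 0.30, s = 0.20, a_s = 0.80. Over all evenings: 0.12 + 0.16 = 0.28. Among craving evenings: 0.28/0.60 = 0.467.

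| Intervention arm (w, s; a_w, a_s) | Acted, given craving | OR, craving evenings | Craved and acted, all evenings | OR, all evenings |
|---|---|---|---|---|
| 1: 0.10, 0.20; 0.30, 0.80 | 63.3% | 1.97 | 19.0% | 0.60 |
| 2: 0.10, 0.18; 0.25, 0.75 | 57.1% | 1.52 | 16.0% | 0.49 |
| 3: 0.20, 0.20; 0.25, 0.75 | 50.0% | 1.14 | 20.0% | 0.64 |
| 4: 0.30, 0.20; 0.25, 0.75 | 45.0% | 0.94 | 22.5% | 0.75 |
| 5: 0.20, 0.10; 0.25, 0.75 | 41.7% | 0.82 | 12.5% | 0.37 |
| 6: 0.20, 0.10; 0.30, 0.80 | 46.7% | 1.00 | 14.0% | 0.42 |

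Rows 1 to 3 reverse. Rows 4 and 5 keep the direction but are weaker. Row 6, a proportional fall in cravings with resistance unchanged, shows no effect at all. In rows 2 and 3 the sign flips although the intervention raises none of the four rates and lowers both acting rates.

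**Does the random effect help?** A person-intercept logistic model was simulated with 138 per arm (the plan's retained number per condition), 4 evenings, 200 replicates, and a between-person standard deviation of 1 on the logit of acting.
- Row 1: median OR 1.94 on craving evenings, nominally significant harm in about 80% of replicates; 0.56 on all evenings.
- Row 2: 1.49, above 1 in 95% of replicates; 0.46 on all evenings.
- Row 5: 0.78; 0.34 on all evenings.

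The person intercept does not remove the reversal.

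**Loss of people.** With 4 evenings per period, taken as independent, the chance that a person has no item 3 answer is (1 − p)^4 at craving rate p: 0.40^4 = 2.6% at p = 0.60, 0.70^4 = 24% at p = 0.30, and 0.80^4 = 41% at p = 0.20. An arm with fewer cravings also contributes fewer people.

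**The case against.** **The denominator is inferred.** The plan never says that no-craving evenings are dropped. A skip rule governs what is asked, not how a blank is coded, and the wording about the odds of indulging could fit an all-reports outcome. This stands in part: if the team meant to score those evenings 0, the problem disappears. But nothing says so, and a blank outcome is excluded by default.

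**Reversal is not assured.** A reader might infer that the sign would be wrong. The documents do not support that. Reversal needs the interventions to remove mainly cravings that are less likely to be acted on, without a matching fall in how often the rest are acted on. The ban limits availability at work and the coaching covers substitute drinks and tools for cravings, so both may also reduce acting on a craving. In the pilot, participants with stronger cravings cut intake by 19.21 oz/day in the multilevel arm against 2.49 oz/day with the ban alone. That is consumption per person, not acting per evening, but it does not suggest that strong cravings are left untouched. This objection stands.

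**Water scored as indulging.** Item 3 also offers "Yes, water, a sugar-free drink, or a drink with no added sugar", and a reader might infer that any affirmative answer counts. Section (4b) describes the information sought as SSB intake in response to a craving, and the Aim 3 research design names the measure in the same terms. The intended meaning is therefore clear, and this is not a defect.

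**Limited reach.** Aim 3 is exploratory. The mediator in the model is the yes/no craving item, Path B uses the change in the proportion of responses reporting a craving, and Path C' uses craving change. The research design mentions SSB intake after cravings as a possible mediator, but no specified equation carries it beyond Path A. Craving occurrence is modelled as well, so a fall in cravings would be visible beside an odd acted-upon result. This stands.

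**The alternative mixes two things.** An all-evenings outcome merges fewer cravings with better resistance, and scores SSB drinking without a craving as 0. This is true, and is a reason to report both quantities, each with its denominator.

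**Conclusion.** The point holds in limited form. Taken literally, the acted-upon comparison between arms in Path A is restricted to evenings selected by a post-randomisation event that the interventions target, so it is not a comparison of randomised groups. Under the assumed rates the OR among craving evenings runs from about 0.8 to 2.0, against 0.37 to 0.75 over all evenings. In every case tried, the restricted comparison understates, hides or reverses the benefit on the all-evenings outcome. Which of these would happen depends on craving and acting rates that the documents do not give.

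The conclusion rests on two readings: that blanks are left uncoded, and that cravings do fall as hypothesised. It affects only the exploratory acted-upon outcome in Path A. The craving-occurrence outcome, Path B, Path C', and Aims 1 and 2 are not touched. It should be corrected before analysis.

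**What to change.** Add one coding rule to the Analytic Plan for Aim 3. For comparisons between arms, define the outcome on every answered evening as 1 if a craving was reported and the sugary-drink box in item 3 was ticked, and 0 otherwise, including evenings with no craving. Label it *craved and drank an SSB*. An evening with both drink boxes ticked scores 1.

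Report the rate among craving evenings alongside it, with its denominator, as descriptive and not a randomised comparison. Because the all-evenings outcome does not separate fewer cravings from better resistance, interpret it next to the craving-occurrence model.

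The cost is a few sentences in the plan, with no new items or data. The rule restores the comparison of randomised groups among answered evenings; it does not address texts that go unanswered.
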